8.1. Administrative procedures

8.1.1. Collection of demographic data

Record demographic data such as date of birth, sex, race, and ethnicity in the participant's eCRF.

Collection of sex, race, and ethnicity data is necessary to assess and monitor the diversity of the trial participants and to determine if the trial participants are truly representative of the impacted population.

8.1.2. Medical history

Obtain the participant's medical history by interviewing the participant/participant's LAR and/or by reviewing the participant's medical records. Record in the eCRF any pre-existing conditions and signs and/or symptoms present prior to the first dose of study intervention including urological or other data pertaining to symptoms which might confound interpretation of urinary symptoms.

8.2. Efficacy assessments

Planned time points for evaluation of clinical symptoms and the measure of clinical efficacy are provided in the SoA.

8.2.1. Clinical symptom score (CSS) and clinical outcomes

Clinical symptoms of uUTI will be recorded based on a participant interview at the time points in the SoA (Section 1.3) using the CSS and instructions in Appendix Section 10.1. At Baseline, the participant must present with at least 2 clinical symptoms of uUTI (i.e., a total CSS ≥ 2 ; Section 5.1). Symptom improvement is defined as a ≥ 1 point decrease in the CSS total score at 24 ± 4 hours.

During Visit 1, the CSS will be conducted by VRCC via telephone call interview while the participant is onsite prior to the first dose of study intervention as per the SoA (Section 1.3) using the CSS and instructions in Section 8.2.1 and Appendix Section 10.1. The CSS will be reviewed (but not remeasured) by a study physician or otherwise appropriate medically trained staff from the study site onsite along with determination of whether other eligibility criteria are met before the first dose of study medication (Appendix Section 10.1). Only if VRCC cannot do the telephone call, then the study site will ask the CSS questions and complete the ~~CCI~~ ~~CCI~~ before the first dose of study intervention. Only one CSS is to be performed at baseline. The same CSS scorer will be

used at all other assessment time points (i.e, visits 2, 3, 4 and 5) for each participant, on all occasions, whenever possible. CSS at visit 6 will be performed by a study physician or otherwise appropriate medically trained staff from the study site (Appendix Section 10.1). The CSS score will be used to programmatically determine the clinical outcome.

[figure not shown]
Table 4 Clinical improvement and resolution at 24 ±4 hours (Visit 2)

Defining Criteria	Outcome
Resolution of clinical signs and symptoms of uUTI present at Baseline (i.e., reduction of total CSS to 0), without the participant receiving other systemic antimicrobials (not for current uUTI) prior to the 24 ±4 hours (Visit 2) assessment and without receiving other systemic antimicrobials for the current uUTI prior to or 24 ±4 hours (Visit 2).	Clinical resolution
Clinical symptom improvement of at least one point at 24 ±4 hours (Visit 2) from Baseline, without the participant receiving other systemic antimicrobials (not for the current uUTI) prior to the 24 ±4 hours (Visit 2) assessment and without receiving other systemic antimicrobials for the current uUTI prior to or 24 ±4 hours (Visit 2).	Clinical improvement

Table 5 Clinical improvement and resolution at 48 ±4 hours (Visit 3), 72 ±4 hours (Visit 4), 96 ±4 hours (Visit 5), and CCI (Visit 6)

Defining Criteria	Outcome
Resolution of clinical signs and symptoms of uUTI present at Baseline (i.e., reduction of total CSS to 0), without the participant receiving other systemic antimicrobials (not for the current uUTI) prior to the assessment at each timepoint and without receiving other systemic antimicrobials for the current uUTI prior to or at each timepoint.	Clinical resolution
Clinical symptom improvement at least one point from Baseline, without the participant receiving other systemic antimicrobials (not for the current uUTI) prior to the assessment at each timepoint and without receiving other systemic antimicrobials for the current uUTI prior to or at each timepoint.	Clinical improvement

CCI

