5.1. Inclusion criteria

Participants are eligible to be included in the study only if all of the following criteria apply:

Age and weight

1. The participant is ≥ 12 years of age at the time of signing the ICF/IAF and has a body weight ≥ 40 kg.

Note: Although participants as young as 12 years of age may enroll in the study, study sites must follow their IRB guidelines. Enrollment will be contingent upon such approvals regarding the allowed lower age limit for clinical study participants.

Type of participant and disease characteristics

2. The participant has 2 or more of the following clinical symptoms of uUTI with onset <96 hours prior to study entry: dysuria, frequency, urgency, or lower abdominal pain based on investigator assessment (see Appendix Section 10.1).
3. The participant has nitrite or pyuria (presence of 3+/large leukocyte esterase) from a pretreatment clean-catch midstream urine sample per local laboratory procedures.

Sex

4. The participant is female.

Contraceptive use is to be consistent with local regulations regarding the methods of contraception for those participating in clinical studies.

- A female participant is eligible to participate if she is a WOCBP who is not pregnant as confirmed by a high sensitivity urine pregnancy test predose at baseline regardless of current or prior contraception use or abstinence, is not breastfeeding, or is not a WOCBP as defined in Appendix Section 10.3.1.2.

Note: Collection of pregnancy information, contraceptive guidance, and WOCBP definitions are provided in Appendix Section 10.3, and requirements for pregnancy testing during and after study intervention are located in Appendix Section 10.7.

- The investigator is responsible for review of medical history, menstrual history, and recent sexual activity to decrease the risk for inclusion of a woman with an early undetected pregnancy.

Informed consent

5. The participant is capable of giving documented informed consent/assent as described in Appendix Section 10.9.3, which includes compliance with the requirements and restrictions listed in the ICF/IAF and in this protocol.

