## Overview of Study Design and Key Features

**Figure 1** Study design overview

<pre> graph LR     V1[Visit 1 (Baseline/Day 1)a (Onsite)] --> S1[Eligibility: - Female participants - ≥12 years of age - CSS ≥2 total score - Nitrite or pyuria (presence of 3+/large leukocyte esterase) from a pretreatment clean-catch midstream urine sample]     S1 --> SI[Study Intervention: Gepotidacin 1500 mg orally BID for 5 daysb]     SI --> OTV[On-treatment Visits (Visit 2, Visit 3, Visit 4, and Visit 5) (Telephone)]     OTV --> V6[Visit 6 CCI (Telephone) Safety follow-up and CSSc]     V6 --> V7[Visit 7 (Follow-up/Day 28±3) (Telephone) Safety follow-up]   </pre>	
	
a. During Visit 1, prior to first dose of study intervention, the Virtual Research Coordination Center (VRCC) will contact the participant by telephone to perform the CSS assessment and CCI CCI (in that specific order). This will be used as the Baseline CSS. The CSS will be reviewed (but not remeasured) by a study physician or otherwise appropriate medically trained staff from the study site onsite along with determination of whether other eligibility criteria are met before the first dose of study medication. Only If VRCC cannot do the telephone call, then the study physician or otherwise appropriate medically trained staff from the study site will ask the CSS questions and complete the CCI CCI before the first dose of study intervention. Only one CSS and CCI is to be performed at Visit.
 
b. The first dose of study intervention will be administered at the study site during Visit 1; the remaining 9 doses over the 5-day treatment course will be self-administered as outpatients. Each dose is to be taken after food consumption and with water to assist with tolerability.
 
c. At Visit 2, Visit 3, Visit 4, and Visit 5, the CSS assessment and CCI CCI will be completed (in that order) by VRCC. CCI CCI

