#### **4.1.2. Baseline Definition**

For all endpoints the baseline value will be the latest pre-dose assessment with a non-missing value, including those from unscheduled visits. If a participant is in the ITT but hasn't taken a dose, they will be included in study population summaries on ITT set.

However, their change from baseline in CSS and **CCI** values will not be included in all the efficacy summary tables based on the CE sets. If time is not collected, Day 1 assessments are assumed to be taken prior to first dose and used as baseline.

If any participant is enrolled with a baseline CSS score < 2, it will be flagged as a protocol deviation and such participants will be excluded from the ITT and all CE analysis sets. If they have taken the dose, then they will be included in the safety analysis set.

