### 4.2.1. Definition of primary endpoint

The primary efficacy endpoint is achieving clinical symptom improvement (including clinical resolution). In this study, a participant will be considered to have clinical improvement (including clinical resolution) outcome if they attain either a “Clinical Improvement with Clinical Resolution” outcome or, a “Clinical Improvement without Clinical Resolution” outcome as defined in Table 1. And otherwise, as not improved/failure if they have any other outcomes.

Individual scores will be recorded by a study physician or otherwise appropriately medically trained staff, as recorded in the delegation log. Clinical symptom score (CSS) of acute cystitis participants will be recorded as per the protocol defined SoA using the following scoring system:

Clinical Signs and Symptoms	None	Mild  Symptom is easily tolerated, causing minimal discomfort, and not interfering with everyday activities	Moderate  Symptom is sufficiently discomforting to interfere with normal everyday activities	Severe  Symptom prevents normal everyday activities
	SCORE 0	SCORE 1	SCORE 2	SCORE 3
Dysuria a				
Frequency				
Urgency				
Lower abdominal				

Clinical Signs and Symptoms	None	Mild	Moderate	Severe
	SCORE 0	SCORE 1	SCORE 2	SCORE 3
or suprapubic pain				

a. Dysuria is defined as pain or burning when passing urine.

- The clinical signs and symptoms include dysuria, frequency, urgency, and lower abdominal or suprapubic pain. Each of the signs and symptoms will be scored from 0 to 3.
- At Baseline, the participant must present with at least 2 signs and symptoms and have a total cumulative symptom score  $\geq 2$ . The total cumulative symptom score is derived by summing the score for each individual sign and symptom. If any individual sign and symptom scores are missing, then total symptom score will also be missing. If the participant is missing baseline assessment, they will be considered 'Unable to determine' (refer [Table 1](#)) for outcome at the respective visit.
- The clinical symptoms improvement will be programmatically determined by comparing the total scores of the signs and symptoms of acute cystitis at the 24 hours ( $\pm 4$  hours) to those present at baseline as shown in [Table 1](#).

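### A baseline total CSS of at least 2 is weaker than inclusion criterion 2, so the SAP exclusion rule drops a woman with one mild symptom but keeps one with a single moderate or severe symptom

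*Protocol*

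**What the plan says.** Several places require a count of symptoms:

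- Protocol 5.1, inclusion criterion 2: "The participant has 2 or more of the following clinical symptoms of uUTI with onset <96 hours prior to study entry". The four symptoms are dysuria, frequency, urgency and lower abdominal pain. The investigator judges this, with a pointer to the CSS in Appendix 10.1.
- Protocol 4.1 and the Design Features row of SAP 1.2 also ask for two or more symptoms.
- SAP 4.2.1 asks for both conditions, at least two symptoms and a total of at least 2, but attaches no flag or exclusion to the count.

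Other places use the total score:

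- Protocol 8.2.1: "At Baseline, the participant must present with at least 2 clinical symptoms of uUTI (i.e., a total CSS ≥ 2 ; Section 5.1". The main clause is a count. The parenthesis restates it as a total and cites Section 5.1 as the source.
- SAP 1.2, Figure 1, eligibility box: "CSS ≥2 total score", with no count. The treatment-assignment row of the same overview refers to Figure 1 for eligibility.
- SAP 4.1.2: "If any participant is enrolled with a baseline CSS score < 2, it will be flagged as a protocol deviation". The stated consequence is removal from ITT and from every CE set, while those who were dosed stay in the safety set.

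On the scale itself, SAP 4.2.1 says "Each of the signs and symptoms will be scored from 0 to 3", and the total is the sum of the four items.

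**The concern.** A count and a severity sum are different rules when items run from 0 to 3. Two symptoms always give a total of at least 2, but a total of 2 or 3 can come from one symptom. The total-score rule is therefore strictly weaker than the criterion it is meant to restate.

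The main consequence is in SAP 4.1.2, where the total decides membership of the analysis sets. Two women can fail inclusion 2 in the same way, each with one symptom. If that symptom is mild, the rule takes her out of ITT and every CE set. If it is moderate or severe, the rule leaves her in ITT and, if she takes both doses as prescribed, in CE24. There a one-point fall in that single item counts as improvement. Neither document gives a reason for treating the two differently.

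The gloss in 8.2.1 could also mislead at entry. The baseline CSS is taken once, normally by the VRCC, and site staff review it alongside the other eligibility criteria. A reviewer who relies on the parenthesis applies the weaker rule.

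**Working it through.** **Inputs.** Four items, each 0 to 3, and the total as their sum (SAP 4.2.1; Protocol Appendix 10.1). Count rule: at least two of four symptoms (Protocol 5.1). Flag: total below 2 (SAP 4.1.2). At least 82 evaluable, an assumed 74% improved, and a 95% CI half-width of about 10 points or less (Protocol 1.1).

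**Step 1: the plan's own figure.** The Clopper-Pearson limits with x = 0.74n are Beta⁻¹(0.025; x, n − x + 1) and Beta⁻¹(0.975; x + 1, n − x). The half-width is 10.03 points at n = 81 and 9.97 points at n = 82. The stated 82 is reproduced and is not in dispute.

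**Step 2: compare the two rules over all score patterns.**

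- All patterns: 4⁴ = 256.
- Fewer than two symptoms (all zero, or one non-zero item): 1 + 4 × 3 = 13. At least two symptoms: 256 − 13 = 243.
- Total below 2 (all zero, or one item scored 1): 1 + 4 × 1 = 5. Total at least 2: 256 − 5 = 251.
- Fails the count but passes the total (one item scored 2 or 3): 4 × 2 = 8, which agrees with 251 − 243 and with 13 − 5.
- Meets the count but fails the total: none, because two symptoms give at least 1 + 1 = 2.

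The error therefore runs one way. These are counts of possible patterns, not expected frequencies of participants.

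**Step 3: what SAP 4.1.2 does with each case that fails inclusion 2.**

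| Baseline pattern | Total | Caught by the 4.1.2 flag | ITT and CE sets under 4.1.2 |
|---|---|---|---|
| No symptom | 0 | yes | excluded |
| One mild symptom | 1 | yes | excluded |
| One moderate symptom | 2 | no | ITT kept; CE if adherent |
| One severe symptom | 3 | no | ITT kept; CE if adherent |

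**Step 4: effect on the primary percentage.** Suppose k of 82 are one-symptom participants and the other 82 − k improve at 74%. If all k improve, the shift is k × 0.26/82. If none improves, it is −k × 0.74/82.

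- k = 1: +0.3 or −0.9 points.
- k = 2: +0.6 or −1.8 points.
- k = 4: +1.3 or −3.6 points.
- k = 8: +2.5 or −7.2 points.

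The documents do not give k. The range 1 to 8 is an assumption that shows the scale.

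**The case against.** The strongest reply is that no passage lets a total score replace inclusion 2. The main clause of 8.2.1, "At Baseline, the participant must present with at least 2 clinical symptoms of uUTI", is itself a count, and Protocol 4.1, the SAP's Design Features and SAP 4.2.1 repeat it. Waivers are not permitted. SAP 6.1.3 adds a data review before the database is frozen, to find deviations that may lead to exclusion, and a listing of eligibility deviations. On this view the parenthesis is loose wording with little practical effect.

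Much of this stands, and it rules out several stronger readings that a reader might infer:

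- That a one-symptom woman satisfies 8.2.1. She meets only the gloss and fails the main clause.
- That the site sees only a total. The form in Appendix 10.1 is an item-by-item grid, and the site reviews the CSS as a whole.
- That she would go unflagged and certainly enter CE24. She is missed by the 4.1.2 flag, but the review and listing in SAP 6.1.3 may find her.
- That she lies outside the primary estimand's population. The estimand speaks of suspected uUTI and does not cite inclusion 2.
- That each case moves the result by 1/82 = 1.2 points. That is a ceiling, which is not reached when the rest improve at about 74%.

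The reply does not remove the contradiction. The listing in SAP 6.1.3 draws on the eCRF eligibility page, so a site that relied on the gloss may have recorded inclusion 2 as met. SAP 4.1.2 also states an explicit exclusion rule, and that rule separates participants who fail inclusion 2 in the same way.

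**Conclusion.** The documents contradict themselves. Protocol 8.2.1 (by its gloss), SAP Figure 1 and SAP 4.1.2 use a total that does not match the symptom count in inclusion 2, Protocol 4.1, the SAP's Design Features and SAP 4.2.1. As written, SAP 4.1.2 catches 5 of the 13 patterns that fail the count and misses 8, so one mild symptom is excluded while one moderate or severe symptom is kept.

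The likely effect on the primary estimate is small. Each such participant moves it by about +0.3 or −0.9 points, against a planned half-width of about 10 points and no hypothesis test. This rests on 82 evaluable, 74% improvement in the rest, and few cases; the last is a judgement, since the documents give no number. It also takes the baseline CSS items as the record of which symptoms were present, which the pointer from inclusion 2 to Appendix 10.1 supports. The sample size is unaffected. The point merits correction because the rule for analysis-set membership is inconsistent and can be put right cheaply, not because a large bias is expected.

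**What to change.** 1. Protocol 8.2.1: delete the parenthetical total-score gloss, keep the reference to Section 5.1, and say that at least two of the four CSS items must be scored 1 or more.
2. SAP Figure 1: replace the total-score entry with the symptom count of inclusion 2.
3. SAP 4.1.2: trigger the flag on fewer than two baseline CSS items scored 1 or more. This catches all 13 failing patterns, including the 5 caught now.
4. SAP 4.1.2: state the consequence. Under the current wording the revised flag also removes these participants from ITT and all CE sets, while those dosed stay in the safety set. All who fail inclusion 2 on baseline symptoms are then handled alike.

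The cost is a short wording change in each document and one programming condition. Item scores are already collected and summarised (SAP 4.2.2). The downside is slightly wider post-enrolment exclusion from an ITT set that SAP Section 3 defines as everyone enrolled, so the exception should be stated there too. The documents do not say whether enrolment is complete. If it is, the SAP changes are still worth making before database lock.

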8.3. Safety assessments

Planned time points for all safety assessments are provided in the SoA (Section 1.3).

8.3.1. Physical examination

- A physical examination will be performed at the Baseline Visit (Section 1.3).
 - The examination will include assessments of the respiratory, CV, abdominal, gastrointestinal, neurological, and urogenital systems.
 - Height and weight will be measured and BMI calculated and recorded prior to dosing only at the Baseline Visit.
- Investigators are to pay special attention to clinical signs related to previous serious illnesses.
- If an additional physical examination is performed (i.e., Unscheduled Visit), it may be symptom directed, and any clinically significant changes from Baseline or clinically significant new findings will be reported as AEs.

8.3.2. Vital signs

- Vital signs will be measured at the Baseline Visit (Section 1.3).
- Temperature, systolic and diastolic blood pressure, respiratory rate, and pulse rate will be recorded (before blood collection for laboratory tests).
- Vital signs will be measured in a semi-supine position after 5 minutes of rest.
- If an additional vital sign measurements are obtained (i.e., Scheduled/Unscheduled Visit), clinically significant changes from Baseline will be reported as AEs.

8.3.3. Electrocardiograms

- Triplicate 12-lead ECGs (over an approximate 5- to 10-minute period) will be performed at the Baseline Visit using an ECG machine that automatically calculates the heart rate and measures PR, QRS, QT, and QTc intervals. Refer to Section 7.1.2 for QTc stopping criteria and additional QTc readings that may be necessary.
- This protocol only requires an ECG evaluation at the Baseline Visit. Ideally, ECGs will be obtained before any vital sign measurements or blood draws scheduled on the same assessment day; however, study sites may perform procedures in an order per their standard of care, as long as participants return to a resting state prior to the start of the ECG collections. Subsequent ECGs only need to be triplicate if the initial one is prolonged.
- If an additional ECGs are performed (i.e., Scheduled/Unscheduled Visit), clinically significant parameter changes from Baseline will be reported as AEs.

8.3.4. Clinical safety laboratory tests

- Safety laboratory assessments will be performed at PPD Global Clinical Laboratory.
- Clinical safety laboratory tests will be performed at the Baseline Visit (Section 1.3). See Appendix Section 10.7 for the list of clinical laboratory tests to be performed. If additional clinical safety laboratory tests are performed (i.e., Unscheduled Visit), they may be symptom-directed.
- The investigator must review the laboratory results, document this review, and record any clinically significant changes occurring post-treatment during the study as an AE. The laboratory results must be retained with source documents.
- With the exception of the urine dipstick and pregnancy testing, a central laboratory will be used. Any baseline results received while participants are on-treatment that are exclusionary will be assessed by the medical monitor. The medical monitor will contact the investigator and advise on appropriate action with the study intervention.
- Abnormal laboratory findings associated with the underlying disease are not considered clinically significant unless judged by the investigator to be more severe than expected for the participant's condition.
- All laboratory tests with values considered clinically significantly abnormal during participation in the study are to be repeated until the values return to normal or baseline or are no longer considered clinically significant by the investigator or medical monitor.
 - In the absence of a diagnosis, abnormal laboratory findings assessments or other abnormal results the investigator considers clinically significant will be recorded as an AE or SAE, if they meet the definition of an AE or SAE (Section 10.8.1 and Section 10.8.2, respectively).
 - If such values do not return to normal/baseline within a period of time judged reasonable by the investigator, the etiology will be identified and the sponsor notified.
 - If laboratory values from non-protocol-specified laboratory tests performed at the institution's local laboratory require a change in participant management or are considered clinically significant by the investigator (e.g., SAE or AE), then the results must be recorded.
- All protocol-required laboratory assessments, as defined in Appendix Section 10.7, must be conducted in accordance with the laboratory manual.

